1.2.1.2. GS-US-337-1116

Preliminary data are available for the current study in adolescent subjects Cohort 1 (12 to < 18 years of age; N=10) and pediatric subjects Cohort 2 (6 to <12 years of age; N=12) who enrolled in the PK Lead-in Phase and received an adult clinical dose of LDV/SOF FDC 90 mg/ 400 mg or a reduced dose of LDV/SOF FDC 45 mg/200 mg, respectively. Of note, 2 out of 12 subjects (subject PPD and PPD in Cohort 2 erroneously received a dose of 90 mg/ 400 mg LDV/SOF FDC during the PK Lead-in Phase: Subject PPD received 90 mg/ 400 mg from Day 1 through Day 10 and Subject PPD received 90 mg/ 400 mg from Day 1 through Day 4 followed by the correct dose of 45 mg/ 200 mg for the remainder of the PK Lead-in Phase (Day 5 through Day 10).

Evaluation of PK in Cohort 2 subjects was conducted using data from all 12 subjects; observed LDV, SOF, and GS-331007 (primary SOF metabolite) exposures on Day 10 were used for Subject PPD and exposures were scaled to 45 mg/ 200 mg for Subject PPD (Table 1-4). Mean exposures of LDV, SOF, and GS-331007 in Cohort 1 and 2 subjects were comparable to observed exposures in the adult subjects in the Phase 2/3 LDV/SOF FDC clinical program; thereby confirming the appropriateness of the adult dose (90 mg/ 400 mg) in the adolescent population (12 to < 18 years of age) and 45 mg/ 200 mg in pediatric patients (6 to < 12 years of age) Table 1-3 and Table 1-4. The appropriateness of the 90 mg/ 400 mg LDV/SOF FDC dose in adolescents and 45 mg/ 200 mg LDV/SOF FDC dose in the pediatric patients is further supported by available safety and efficacy data in the treatment phases of the study.

Table 1-3. Steady-state PK and Statistical Comparisons of LDV, SOF and GS-331007 PK in Adolescent Subjects (PK Lead-in) and Adult Subjects (Phase 2/3 Population PK Analysis)

Mean (%CV)	Adolescents (N=10)	Phase 2/3 (N=2113)	GMR% (90% CI)
LDV			
AUC _{tau} (ng*hr/ml)	10200 (50.9)	8530 (60.8)	127 (94.9, 170)
C _{max} (ng/ml)	564 (41.2)	364 (51.4)	162 (125, 209)
C _{tau} (ng/ml)	319 (71.5)	247 (59.2)	128 (95.2, 172)
SOF*			
AUC _{tau} (ng*hr/ml)	2180 (26.6)	1380 (34.0)	160 (138, 185)
C _{max} (ng/ml)	1140 (57.2)	659 (34.0)	156 (127, 190)
GS-331007			
AUC _{tau} (ng*hr/ml)	12700 (13.7)	12500 (29.2)	105 (90.6, 122)
C _{max} (ng/ml)	1010 (21.5)	736 (28.2)	139 (120, 161)

Data reported to 3 significant figures; *N=1542

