3.1.1. PK Lead-in Phase

The PK Lead-in Phase will evaluate and/or confirm the age appropriate LDV/SOF FDC dose by analyzing PK, safety, and antiviral activity of LDV/SOF FDC through 10 days of dosing for each cohort. Children aged 3 to < 6 years, children aged 6 to < 12 years, and adolescents aged 12 to < 18 years with chronic HCV-infection and a HCV RNA \geq 1000 IU/mL at study entry will be evaluated. Subjects must be treatment naïve without history of cirrhosis to participate in the PK Lead-in Phase. Three cohorts of at least 10 subjects each will be sequentially enrolled:

- Cohort 1: 12 to < 18 years old, weighing \geq 45kg
- Cohort 2: 6 to < 12 years old, weighing \geq 17 kg and < 45 kg
- Cohort 3: 3 to < 6 years old
 - At least 4 subjects weighing \geq 17 kg
 - At least 4 subjects weighing < 17 kg

The study will start with Cohort 1. Subjects will receive LDV/SOF FDC (90 mg/ 400 mg adult tablet or 4 \times 22.5 mg/100 mg tablets if determined necessary based on LDV/SOF FDC swallowability assessment) for 10 days with intensive PK conducted on Day 10.

[figure not shown]
Cohort 2: Subjects will receive LDV/SOF FDC 45 mg/ 200 mg (2 \times 22.5 mg/ 100 mg tablets) for 10 days with intensive PK conducted on Day 10.

Cohort 3: Subjects will receive LDV/SOF FDC oral granules; subjects weighing \geq 17 kg will receive LDV/SOF FDC 45 mg/ 200 mg (4 \times 11.25 mg/ 50 mg packets) and subjects weighing <17 kg will receive LDV/SOF FDC 33.75 mg/ 150 mg (3 \times 11.25 mg/ 50 mg packets) for 10 days with intensive PK assessments conducted on Day 10.

Subjects enrolled in the PK Lead-in Phase of each cohort (Cohorts 1, 2, and 3) will immediately enroll in the Treatment Phase as they complete Day 10 of PK Lead-in Phase. They will continue dosing with LDV/SOF FDC with no interruption of study drug administration. Subjects rolling over from the PK Lead-in Phase will not be required to perform the screening, Day 1, or Week 1 visit of the Treatment Phase.

Figure 3-1. PK Lead-in Phase Study Schema

PK Lead-in

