9.4. Pharmacokinetic Analysis

PK analysis will be performed for PK Lead-in phase using the intensive PK Lead-in analysis set.
PPD

The concentration data of LDV, SOF, and metabolites (GS-331007 and GS-566500) over sampling time will be listed and summarized by nominal time and cohort. Pharmacokinetic parameters (e.g., AUC_{τ} , AUC_{last} , C_{max} , T_{max} , C_{last} , T_{last} , C_{τ} , λ_z , CL/F , V_z/F and $t_{1/2}$) will be listed and summarized for LDV, SOF, and metabolites (as applicable) using descriptive statistics (e.g., sample size, arithmetic mean, geometric mean and its 95% confidence interval, coefficient of variation %, standard deviation, median, Q1, Q3, minimum, and maximum) by cohort and overall. Plasma concentrations over time will be plotted in semilogarithmic and linear formats as mean \pm standard deviation and median (Q1, Q3).

To evaluate if the steady-state PK of GS-331007, SOF, and LDV achieved in pediatric subjects of this study are similar to the exposures observed in adult subjects (Table 9-1), the GS-331007, SOF, and LDV exposure data from this study will be compared to the integrated adult data. The primary endpoint of this analysis will be evaluated by carrying out an analysis of variance (ANOVA) for log-transformed GS-331007, SOF, and LDV AUC_{τ} . The 90% confidence intervals will be constructed for the ratio of geometric means of each PK parameters. The equivalence boundary is set as 50% to 200%.

Given that dose ranging studies for SOF established that a dose of 200 mg results in suboptimal exposure compared to the 400 mg dose, and the lack of clinically significant exposure-safety relationships observed across a broad range of GS-331007 and SOF exposure, bounds of 50% to 200% for GS-331007 and SOF AUC_{τ} will allow identification of a clinically relevant difference in exposure in the pediatric population.

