1.2.1. PK Lead-in Phase

The PK Lead-in Phase will evaluate and/or confirm the age appropriate LDV/SOF FDC dose by analyzing PK, safety, and antiviral activity of LDV/SOF FDC through 10 days of dosing.

At least 10 treatment-naïve subjects without history of cirrhosis will be sequentially enrolled into each of the following 3 cohorts:

- Cohort 1: 12 to < 18 years old, weighing ≥ 45 kg
- Cohort 2: 6 to < 12 years old, weighing ≥ 17 kg and < 45kg
- Cohort 3: 3 to < 6 years old
 - At least 4 subjects weighing ≥ 17 kg
 - At least 4 subjects weighing < 17 kg

Intensive PK and safety results through Day 10 of each Cohort will be reviewed to confirm the appropriateness of the LDV/SOF FDC dose for that age group as well as to determine the age-appropriate dose to be evaluated in the PK Lead-in Phase of the next age Cohort.

Subjects enrolled in the PK Lead-in Phase will immediately enroll in the Treatment Phase as they complete Day 10 of PK Lead-in. They will continue dosing with LDV/SOF FDC with no interruption of study drug administration until the appropriateness of the dose is confirmed by PK and safety data from the PK Lead-in Phase.

Cohort 1 subjects received LDV/SOF FDC (90 mg/ 400 mg adult tablet or 4×22.5 mg/100 mg tablets if determined necessary based on LDV/SOF FDC swallowability assessment) for 10 days with intensive PK conducted on Day 10.

Cohort 2 subjects received LDV/SOF FDC 45 mg/ 200 mg (2×22.5 mg/ 100 mg tablets) for 10 days with intensive PK conducted on Day 10.

Cohort 3 subjects weighing ≥ 17 kg received LDV/SOF FDC 45 mg/ 200 mg (4×11.25 mg/ 50 mg packets containing granules) for 10 days with intensive PK conducted on Day 10.

Cohort 3 subjects weighing <17 kg received LDV/SOF FDC 33.75 mg/ 150 mg (3×11.25 mg/ 50 mg packets containing granules) for 10 days with intensive PK conducted on Day 10.

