3.2. Subject Grouping

For analyses based on the All Enrolled Analysis Set or FAS, subjects will be grouped according to the treatment to which they were enrolled. For analyses based on the Safety Analysis Set, subjects will be grouped according to the actual treatment received. The actual treatment received is defined as the enrolled treatment except for subjects who received treatment that differs from the enrolled treatment for the entire treatment duration. In this case, the actual treatment received is defined as the treatment received for the entire treatment duration.

Generally, subjects are analyzed, except for the safety analysis, by treatment groups based on age group, HCV genotype, prior treatment experience, cirrhosis status, and treatment duration:

Table 3-1. Non-safety Treatment Groups*

12 to < 18 Years Old		3 to < 12 Years Old			
LDV/SOF (90/400 mg) 12 Weeks		LDV/SOF (45/200 mg or 33.75/150 mg) 12 Weeks		LDV/SOF (45/200 mg) 24 Weeks	LDV/SOF+RBV (45/200 mg) 24 Weeks
GT1 TN w/ or w/o cirrhosis (N =)	GT1 TE without cirrhosis (N =)	GT1, GT4 TN w/ or w/o cirrhosis (N =)	GT1 TE without cirrhosis (N =)	GT1 TE with cirrhosis (N =)	GT3 TE w/ or w/o cirrhosis (N =)
6 to < 12 Years Old			3 to < 6 Years Old		
LDV/SOF (45/200 mg) 12 Weeks		LDV/SOF (45/200 mg) 24 Weeks	LDV/SOF+RBV (45/200 mg) 24Weeks	LDV/SOF (45/200 mg or 33.75/150 mg) 12 Weeks	
GT1, GT4 TN w/ or w/o cirrhosis (N =)	GT1 TE without cirrhosis (N =)	GT1 TE with cirrhosis (N =)	GT3 TE w/ or w/o cirrhosis (N =)	GT1, GT4 TN w/ or w/o cirrhosis (N =)	

GT = genotype, TN = Treatment Naïve, TE = Treatment Experienced, w/ = with, w/o = without
 *Treatment Groups reflect the subjects actually enrolled.

For the safety analysis, subjects will be analyzed by the following groups based on age group, treatment regimen and duration:

Table 3-2. Safety Treatment Groups

12 to < 18 Years Old	3 to < 12 Years Old		
LDV/SOF (90/400 mg) 12 Weeks (N =)	LDV/SOF (45/200 mg or 33.75/150 mg) 12 Weeks (N =)	LDV/SOF (45/200 mg) 24 Weeks (N =)	LDV/SOF+RBV (45/200 mg) 24 Weeks (N =)
6 to < 12 Years Old			3 to < 6 Years Old
LDV/SOF (45/200 mg) 12 Weeks (N =)	LDV/SOF (45/200 mg) 24 Weeks (N =)	LDV/SOF+RBV (45/200 mg) 24 Weeks (N =)	LDV/SOF (45/200 mg or 33.75/150 mg) 12 Weeks (N =)

Subjects in the 3 to < 6 years of age group will have additional selected efficacy and safety analyses performed according to baseline weight in the following subgroups:

Table 3-3. Subgroups for Selected Analyses in 3 to < 6 years of Age

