8. PHARMACOKINETIC ANALYSES

8.1. PK Analysis in the PK Lead-in Phase (Intensive PK Analysis)

Intensive PK Analysis will be performed using the PK Lead-in Phase Intensive PK Analysis Set. Concentrations of SOF, GS-331007 and LDV from subjects in the PK lead-in Phase over sampling time will be listed and summarized using descriptive statistics (n, arithmetic mean, geometric mean and its 95% confidence interval, coefficient of variation [%CV], SD, median, Q1, Q3, minimum, and maximum) by nominal time and cohort. For Cohorts 1 and 2, plasma samples will be collected for PK analyses following dosing of study drugs on Day 10 at the following time points: 0 (predose), 0.5, 1, 2, 3, 4, 5, 8, and 12 hours postdose. For Cohort 3, plasma samples for PK analyses will be collected at the following time points: 0 (predose), 0.5, 2, 4, 8, and 12 hours postdose. PK parameters from subjects in the PK lead-in Phase will be summarized (e.g; AUC_{τ} , AUC_{last} , C_{max} , T_{max} , C_{last} , T_{last} , C_{τ} , $T_{1/2}$, volume of distribution and clearance, as appropriate) by cohort.

To confirm the appropriateness of LDV/SOF FDC dose for each age group, PK parameters for SOF, GS-331007 and LDV will be compared between each age group from this study and the LDV/SOF FDC NDA patient population (which includes population-PK derived PK exposure data from adult Phase 2 and 3 studies) by carrying out an analysis of variance (ANOVA) for log-transformed AUC_{τ} of GS-331007 and LDV as the primary endpoint and C_{max} of GS-331007 and LDV as a secondary endpoint. Geometric Mean Ratio and its 90% confidence interval will be provided.

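### Cohort 3 holds two weight-based doses but is compared with adults as one age group, so the pooled exposure ratio can lie within 50%-200% while one dose is off target.

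*SAP*

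**What the plan says.** Protocol 3.1.1 and SAP 1.2.1 give Cohort 3 (3 to <6 years) two doses by weight: "Cohort 3 subjects weighing ≥ 17 kg received LDV/SOF FDC 45 mg/ 200 mg" and "Cohort 3 subjects weighing <17 kg received LDV/SOF FDC 33.75 mg/ 150 mg". Cohort size is set by "Three cohorts of at least 10 subjects each will be sequentially enrolled", with a floor in each band, for example "At least 4 subjects weighing < 17 kg".

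The comparison with adults does not follow that split. SAP 8.1 summarises PK by cohort and says "PK parameters for SOF, GS-331007 and LDV will be compared between each age group from this study and the LDV/SOF FDC NDA patient population", using an ANOVA on log AUCtau with a GMR and 90% CI. It gives no acceptance limits. Those are in Protocol 9.4: "The equivalence boundary is set as 50% to 200" percent. Protocol 9.4 also summarises by cohort and overall.

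The SAP does split this age group by weight elsewhere. SAP 3.2 says "Subjects in the 3 to < 6 years of age group will have additional selected efficacy and safety analyses performed according to baseline weight", with the groups in Table 3-3, but it names efficacy and safety only and not PK.

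Protocol 9.4 has two further provisions. If more than one subject in a cohort has an AUCtau below the adult 2.5th percentile, the cohort's dose may be reassessed. It also says in one line, with no model or criterion, that the effect of dose on PK will be assessed; SAP 8.1 plans no such analysis.

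**The concern.** The primary objective of the PK Lead-in is to confirm the dose, and for the youngest children there are two doses to confirm. Protocol 1.5 sets each one separately, by scaling adult exposure to body weight. Pooling takes for granted what the Lead-in is meant to check, namely that the two bands reach similar exposure. A pooled geometric mean averages across doses, so a shortfall or excess at one dose is diluted by the other, and errors in opposite directions cancel. What is at stake is whether the reported result supports a statement about each dose or only about their average.

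**Working it through.** **Inputs.** Adult AUCtau CVs from Protocol Table 9-1: GS-331007 29.2% (N = 2113), SOF 34.0% (N = 1542), LDV 60.8% (N = 2113). Cohort of 10 with at least 4 per band, so splits run from 4:6 to 6:4. Bounds 50%-200% and a 90% CI from Protocol 9.4. SAP 8.1 names only GS-331007 and LDV for the ANOVA, so the SOF figures rest on Protocol 9.4.

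**Formulas.** Log SD: s = sqrt(ln(1 + CV²)) = 0.286, 0.331, 0.561. The 90% CI is GMR × exp(±h), with h = 1.645 × s × sqrt(1/n + 1/N).

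**The plan's own figures.** For Cohort 2 (n = 12), GS-331007 with GMR 65.2% gives 56.9-74.7, as printed in Table 1-4. LDV gives 66.5-113.5 against 66.5-114 printed. SOF comes out slightly wide (99.1-135.8 against 101-133). Protocol 9.4 says that the CI stays within 50%-200% with doubled variability or a 30% difference. At n = 10 this holds. For LDV, the tightest case, doubled CV gives 60.9-164.3, -30% gives 52.3-93.8 and +30% gives 97.0-174.2.

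**What the pooled comparison lets through.** At n = 10 the pooled CI lies inside the bounds when the pooled GMR is between 50·exp(h) and 200·exp(-h). With k children in the off-target arm and the other arm at 100%, pooled ln GMR = (k/10) × ln(arm GMR). The extreme arm GMR is therefore (pooled limit)^(10/k).

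| | Pooled limits | Arm of 4 | Arm of 5 | Arm of 6 |
|---|---|---|---|---|
| GS-331007 | 58.0-172.3% | 25.7-390% | 33.7-297% | 40.4-248% |
| SOF | 59.4-168.3% | 27.2-367% | 35.3-283% | 42.0-238% |
| LDV | 67.0-149.3% | 36.7-272% | 44.9-223% | 51.3-195% |

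For example, GS-331007 at the lower limit with 4 children: 0.580^2.5 = 0.257.

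**Worked case.** Four children at 45% and six at 100%: pooled GMR = 0.45^0.4 = 72.7%. The pooled CI is 62.6-84.3 (GS-331007), 61.1-86.3 (SOF) or 54.2-97.3 (LDV), all inside the bounds. The arm's own CIs are 36-57, 34-59 and 28-71. Five at 45% and five at 220% pool to sqrt(0.45 × 2.20) = 99.5%.

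**With the 2.5th-percentile rule.** Simulated cohorts of 10, four off target and six at 100%, lognormal with adult log SD:

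| | GS-331007 | SOF | LDV |
|---|---|---|---|
| Four at 45%: pooled passes | 0.99 | 0.97 | 0.68 |
| Rule fires | 0.98 | 0.91 | 0.40 |
| Pooled passes and rule silent | 0.02 | 0.09 | 0.50 |
| Four at 220%: pooled passes | 0.99 | 0.98 | 0.69 |
| Pooled passes and rule silent | 0.99 | 0.97 | 0.68 |

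At 220% the rule fires in only about 1% of cohorts.

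**Precision of a 4-child arm.** exp(h) at n = 4 is 1.27 (GS-331007), 1.31 (SOF) and 1.59 (LDV). An LDV interval then fits inside 50%-200% only if the observed GMR is 79.3-126.0%. For a dose exactly on target, the SE is 0.561/2 = 0.281 and ln 1.26 = 0.231. The chance of fitting is 2Φ(0.231/0.281) - 1, about 59%.

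**The case against.** **A safeguard exists.** The 2.5th-percentile rule is in the same section as the bounds, and for low GS-331007 or SOF it would nearly always prompt a look. That stands. A reader might infer that the plan can hide any failure of either dose, and on the low side for those two analytes this is largely untrue. The rule is weaker for LDV, has no upper limit, is discretionary, and acts on the cohort and not on a dose.

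**The extreme limits need implausible clearance.** The doses stand 3:4. With AUC = dose/clearance, the lighter band at 45% against 100% needs 0.75/0.45 = 1.67 times the heavier band's apparent clearance, and at 26% it needs 0.75/0.257 = 2.9 times. With equal clearance, a pooled GMR that only just passes leaves a 4-child lighter band at pooled limit × 0.75^0.6: 49% (GS-331007), 50% (SOF) or 56% (LDV). So the extremes mark what the comparison cannot exclude, not what to expect. Even so, the weight scaling is the premise under test.

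**Masking depends on the split.** True. With 6 children off target, no LDV value outside 50%-200% is masked at expected values.

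**Dose confirmation is broader than one test.** The protocol confirms dose by reviewing intensive PK and safety results, lists individual PK parameters, and mentions a dose-effect assessment; SAP 8.2 adds population PK. This stands as context, but none of these specifies an adult comparison by dose. SAP 1.2.2 speaks of the confirmed dose in the past tense, so the point concerns what is reported, not what was given.

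**Cohort 2.** A reader might see the same fault there, because the protocol records that two children "in Cohort 2 erroneously received a dose of 90 mg/ 400 mg LDV/SOF FDC during the PK Lead-in Phase". The documents do not support that. One of them had returned to 45/200 mg by Day 5. Leaving the other unscaled would raise a GMR by 2^(1/12) = 1.06. Protocol 1.2.1.2 reports scaling for that child, and the Table 1-4 footnote reports similar results without both children.

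**Conclusion.** The point holds in a limited form. As written, the adult comparison for ages 3 to <6 years answers for the average of two doses. With 10 children and the other arm at 100%, it can pass with a 4-child arm at about 26%, 27% or 37% (GS-331007, SOF, LDV) or at 390%, 367% or 272%. With 6 children in the off-target arm the lower limits rise to 40%, 42% and 51%. The gaps that remain after the 2.5th-percentile rule are low LDV (missed in about half of cohorts with four children at 45%) and high exposure for all three analytes.

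Three stronger readings are not supported. The documents contain no Cohort 3 PK results, so nothing shows that either dose is off target. The pooled ratio is not the only evidence in the dose review. Nor does it follow that each band should face its own pass/fail test, because four children cannot support one for LDV.

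Assumptions: paediatric log SD equal to adult, lognormal AUCtau, 10 children, unweighted pooling, and the adult 2.5th percentile taken from a lognormal. Parts of the protocol's PK text are redacted and may say more.

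**What to change.** In SAP 8.1 and Protocol 9.4, report the AUCtau summary, GMR and 90% CI against adults separately for the two Table 3-3 weight/dose groups, beside the pooled 3 to <6 year row. Read the separate rows descriptively against 50%-200%. State any dose-confirmation conclusion with reference to both dose rows and not to the pooled row alone.

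Say in advance that intervals will be wide: with 4 children, a factor of about 1.27 (GS-331007), 1.31 (SOF) or 1.59 (LDV) either way. An LDV interval that crosses a bound is then not by itself a failure.

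The cost is a few sentences and table rows, with no new data. No change is needed for Cohort 2, and no view is taken on which dose is right.

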Table 1-4. Steady-state PK and Statistical Comparisons of LDV, SOF and GS-331007 PK in Pediatric Cohort 2 Subjects (6 to <12 years old; PK Lead-in) and Adult Subjects (Phase 2/3 Population PK Analysis)

Mean (%CV)	Pediatrics (N=12)**	Phase 2/3 (N=2113)	GMR% (90% CI)
LDV			
AUC _{tau} (ng*hr/ml)	7520 (58.0)	8530 (60.8)	86.9 (66.5, 114)
C _{max} (ng/ml)	432 (51.3)	364 (51.4)	116 (92.1, 147)
C _{tau} (ng/ml)	248 (67.5)	247 (59.2)	91.1 (69.5, 120)
SOF*			
AUC _{tau} (ng*hr/ml)	1600 (29.7)	1380 (34.0)	116 (101, 133)
C _{max} (ng/ml)	906 (36.0)	659 (34.0)	139 (116, 167)
GS-331007			
AUC _{tau} (ng*hr/ml)	8140 (31.6)	12500 (29.2)	65.2 (56.9, 74.7)
C _{max} (ng/ml)	772 (24.4)	736 (28.2)	106 (92.8, 122)

Data reported to 3 significant figures; *N=1542 (Phase 2/3), ** Similar results were observed following exclusion of subjects PPD and PPD who received LDV/SOF 90 mg/400 mg during the PK-Lead-in

Please refer to the Investigator's Brochure (IB) for additional information on the LDV/SOF FDC including:

- In Vitro Anti-Hepatitis C Virus Activity
- Nonclinical Pharmacokinetics and In Vitro Metabolism
- Nonclinical Pharmacology and Toxicology
- Clinical Experience

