9.1.2. Primary Endpoints

For the PK Lead-in Phase, the appropriateness of the LDV/SOF FDC dose will be assessed by evaluating the steady-state PK of the LDV/SOF FDC. The primary endpoint for determining steady state PK is AUC_{τ} of GS-331007, SOF, and LDV. Additional steady-state PK parameters of GS-331007, SOF, and LDV (e.g., AUC_{last} , C_{max} , T_{max} , C_{last} , T_{last} , C_{τ} , λ_z , CL/F , V_z/F and $t_{1/2}$) will be estimated and summarized as described in Section 9.4.

For the Treatment Phase, the primary safety endpoint is any AE leading to permanent discontinuation of study drug (s).

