1. INTRODUCTION

This statistical analysis plan (SAP) describes the statistical analysis methods and data presentations to be used in tables, figures, and listings (TFLs) in the clinical study report (CSR) for Study GS-US-337-1116. This SAP is based on the study Protocol Amendment 6 dated 08 June 2017 and the electronic case report form (eCRF). The SAP will be finalized before database finalization. Any changes made after the finalization of the SAP will be documented in the CSR.

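### SAP 8.1 leaves SOF out of the ANOVA that compares exposure with adults, although the protocol makes SOF AUCtau one of three primary PK endpoints

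*SAP*

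**What the plan says.** **Protocol.** Section 9.1.2 states: "The primary endpoint for determining steady state PK is" "AUC_{τ} of GS-331007, SOF, and LDV". Section 9.4 specifies an ANOVA on log-transformed AUCtau of the same three analytes against integrated adult data, with 90% CIs for the geometric mean ratios. It fixes the criterion: "The equivalence boundary is set as 50% to 200" percent. It then justifies the criterion for SOF by name, referring to "bounds of 50% to 200% for GS-331007 and SOF" AUCtau, and gives a separate argument for LDV.

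**SAP.** Section 8.1 begins its comparison sentence with "PK parameters for SOF, GS-331007 and LDV will be compared between each age group from this study" and the adult population. The same sentence then gives the method: an ANOVA of log AUCtau "of GS-331007 and LDV as the primary endpoint", with Cmax of those same two analytes as secondary. It promises a GMR and a 90% CI and names no boundary; 50% to 200% appears nowhere in the SAP.

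**Declared changes.** The SAP introduction says "This SAP is based on the study Protocol Amendment 6". Sections 6.4 and 7.10 report no changes to the efficacy and safety analyses. Section 8 has no equivalent statement for PK, and the revision table in section 11 is empty.

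**The concern.** The SAP sentence promises a comparison of three analytes by means of an ANOVA of two. A programmer working from the method clause would produce no GMR or interval for SOF, and so would leave out a comparison that the protocol classes as primary for dose confirmation. The descriptive SOF summaries in SAP 8.1 and the population PK model in 8.2 are not the protocol's test against a boundary.

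This would matter little if GS-331007, a metabolite of SOF, tracked SOF exposure closely. The trial's own data show that it does not. A secondary point is that an interval reported without its criterion can be judged against a different one. Protocol 1.2.1.1.2, for example, used 80–125% for GS-331007 in the granules food-effect comparison.

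**Working it through.** **1. The protocol's own precision statement.** Protocol 9.4 says that with 2-fold higher variability, or a 30% difference in AUCtau, the 90% CIs stay within 50–200%. Inputs are the adult CVs in Table 9-1 (GS-331007 29.2%, N = 2113; SOF 34.0%, N = 1542; LDV 60.8%, N = 2113) and the minimum of 10 subjects per cohort. With log-SD = √ln(1 + CV²), CI = GMR × exp(± q × SE), and the most conservative quantile tried (t with 9 df, variances not pooled):

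| Scenario | GS-331007 | SOF | LDV |
|---|---|---|---|
| 2-fold variability, GMR 100% | 73.0–136.9 | 69.9–143.0 | 57.5–173.8 |
| GMR 70% | 59.3–82.7 | 57.8–84.8 | 50.5–97.0 |
| GMR 130% | 110.1–153.5 | 107.3–157.6 | 93.8–180.1 |

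All lie inside 50–200%, so the statement reproduces. It covers SOF.

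**2. Reported AUCtau results (Protocol Tables 1-3 and 1-4), GMR % (90% CI).**

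| Analyte | Cohort 1 (n = 10) | Cohort 2 (n = 12) |
|---|---|---|
| SOF | 160 (138, 185) | 116 (101, 133) |
| GS-331007 | 105 (90.6, 122) | 65.2 (56.9, 74.7) |
| LDV | 127 (94.9, 170) | 86.9 (66.5, 114) |

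All six intervals lie inside 50–200%. SOF in Cohort 1 comes closest to the upper bound (185; the next is LDV at 170).

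**3. Does GS-331007 stand in for SOF?** SOF GMR divided by GS-331007 GMR:
- Cohort 1: 160/105 = 1.52
- Cohort 2: 116/65.2 = 1.78

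In Cohort 2 the two analytes lie on opposite sides of 100%.

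**4. Variance of the SOF comparison.** Back-solving the pooled log-SD from the reported SOF intervals, with t quantile 1.646:
- Cohort 1: [ln(185/138)/2] / [1.646 × √(1/10 + 1/1542)] = 0.281
- Cohort 2: [ln(133/101)/2] / [1.646 × √(1/12 + 1/1542)] = 0.289
- From the adult CV of 34.0%: √ln(1 + 0.34²) = 0.331

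**5. Room for SOF in Cohort 3.** Assume n = 10, pooled ANOVA and log-SD 0.28 to 0.331. The log half-width is 1.646 × SD × √(1/10 + 1/1542) = 0.146 to 0.173.
- Largest GMR that passes: 200/exp(half-width) = 172.8% to 168.3%
- Smallest GMR that passes: 50 × exp(half-width) = 57.9% to 59.4%

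A repeat of the Cohort 1 value of 160% would pass by a small margin.

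**6. Role of the boundary.** SOF in Cohort 1 (138–185) and GS-331007 in Cohort 2 (56.9–74.7) meet 50–200% but would not meet 80–125%.

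**The case against.** The strongest reply is that this is a drafting slip. SOF is named at the start of the same sentence. Tables 1-3 and 1-4 already report SOF ratios with 90% CIs. In the granules study, LDV and GS-331007 were labelled primary and SOF ratios were still tabulated. This makes a slip plausible, but the method clause still lacks SOF. If it is a slip it needs correcting; if it is deliberate it needs declaring.

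Second, the boundary stands in the protocol and the SAP states no competing one. That is fair: not repeating it would not be a finding on its own.

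Third, SAP 1.2.2 describes dose confirmation in each age group in the past tense, so Cohort 3 confirmation may already have been complete when the SAP was written. This stands. It limits the effect to what the final report contains.

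Fourth, the Cohort 3 window borrows variability from adults and from tablet cohorts, whereas Cohort 3 takes granules at two weight-based doses with a sparser sampling schedule. If the SD doubles and variances are not pooled, step 1 implies a window of about 50/0.699 = 71.5% to 200/1.430 = 140%, and 160% would fail. The planned ANOVA pools variance, however, and about 1,542 adults dominate it. With a doubled pediatric CV (log-SD √ln(1 + 0.68²) = 0.617), the pooled log-SD is √[(9 × 0.617² + 1541 × 0.331²)/1550] ≈ 0.33, so the window in step 5 is essentially unchanged. Pooled ANOVA from the adult CVs also closely reproduces the reported LDV and GS-331007 intervals, which supports reading the plan that way.

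Finally, the protocol copy reviewed has no title page, so it could not be confirmed as Amendment 6. Nothing in the text suggests a version in which SOF was not a primary analyte.

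**Conclusion.** The point holds. The SAP's stated method omits one of the three comparisons that the protocol makes primary for the PK Lead-in, and the omission is not declared. It is a specification gap that should be closed. It does not overturn a result: SOF passes in Cohorts 1 and 2, and sample size, power and alpha are unaffected. The gap matters because SOF ran 1.52 and 1.78 times GS-331007 relative to adults and had the AUCtau interval nearest the upper bound, so results on the two retained analytes do not show where SOF lies. The open exposure is Cohort 3 and the final PK report. The passing window of about 58–59% to 168–173% for Cohort 3 assumes 10 subjects, a pooled-variance ANOVA and a log-SD of 0.28 to 0.33. The missing boundary is a minor addition.

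**What to change.** In SAP 8.1, add SOF to the analytes named for the primary AUCtau ANOVA, so that the method matches the opening of its own sentence and Protocol 9.1.2 and 9.4. Add one sentence saying that each 90% CI will be judged against the 50% to 200% boundary of Protocol 9.4. If SOF was removed on purpose, add to section 8 a statement of changes from the protocol-specified PK analysis and give the reason there.

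The cost is one clause, one sentence and SOF rows in an existing table. SOF AUCtau is already derived, so no new data, sampling or subjects are needed.
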